The active placebo in this study will be a low dose of the investigational drug. Active placebo dose of psilocybin was chosen on the basis of early and recent studies of psilocybin in humans (Hasler et al. 2004; Isbell 1959; Moreno et al. 2006; Passie et al. 2002). This dose was chosen for its ability to produce a few of the effects of psilocybin without producing any of the potentially therapeutic effects. People may perceive lights or colors as being brighter and sounds as being different, and they may experience slight changes in mood, cognition or perception. A 4 mg dose of psilocybin is not expected to generate a mystical or transformative experience.

Sample Population and Subjects

The study will enroll nine (9) individuals with the following criteria listed below. Study drop-outs or withdrawals will be replaced until nine participants have completed the randomized phase of the study. Study completion will be defined as attending visits from screening up through the follow-up two weeks after the second psilocybin-assisted session. Participants who are unable to complete or withdraw from the open-label phase or before the two-month follow-up phase will not be replaced. Inclusion Criteria

Inclusion Criteria

Prospective participants must meet the following inclusion criteria listed below to be eligible for study enrollment.

1. Have been diagnosed with Stage IV melanoma with a life expectancy of one year or less
2. Meet diagnostic criteria for anxiety on the SCID, or a score of 8 or higher on the HADS Anxiety score.
3. Diagnosis must be a new diagnosis of anxiety subsequent to diagnosis with melanoma.
4. Are 18 years or older,
5. Live with another adult who is their primary caregiver, who can also provide transportation to and from the cancer center for each experimental session and who also consents to take part in a parallel investigation of anxiety and depression in primary caregivers. The same caregiver may remain overnight with participants after each psilocybin session.
6. Have a Mini-Mental State Exam score of 27 or higher.
7. Are willing to commit to medication dosing, experimental sessions with overnight stay, traveling to follow-up sessions, and to complete the evaluation instruments.
8. Are willing to refrain from taking any anti-depressants during the study period.
9. Are willing to refrain from taking any benzodiazepines during the 24 hours preceding each scheduled psilocybin, placebo, or open label session.

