10. Are able to communicate in English.

Exclusion Criteria

Prospective participants with the following conditions will be excluded:

1. Meet DSM-IV criteria for bipolar disorder, schizophrenia, or other psychotic disorders.

2. Meet DSM-IV criteria for abuse of or dependence on any substance (other than caffeine or nicotine) in the past 60 days.
3. Have first-degree relatives (as parent or full sibling) with past or present psychiatric disorders, including schizophrenia, bipolar affective disorder and other psychoses, but excluding mood disorders.
4. Cannot have a current diagnosis of anxiety disorder that predates diagnosis with melanoma.
5. Have used psilocybin or psilocybin-containing mushrooms within the past year.
6. Require concomitant treatment with anti-psychotic medications, prescribed for the management of either psychiatric symptoms or nausea. The restriction on 5HT_{2C}/5HT₃ antagonists is applicable for 24 hours before and including the day of the study.
7. Are cachectic as indicated by loss of 10% or greater of their total weight.
8. Have been diagnosed with primary or metastatic cancer of the CNS confirmed by MRI, within 6 weeks of participation in the study.
9. Have uncontrolled hypertension.
10. Have baseline laboratory values indicative of severely compromised hepatic function, indicated by unacceptable levels of alkaline phosphatase (ALP) above 750 U/L. Participants must also have laboratory blood screening indicating ALP below 750 U/L immediately prior to administration of psilocybin.
11. Are women who are pregnant or nursing, or of child bearing potential and are not practicing an effective means of birth control.
12. Are reasonably judged to present a serious suicide or homicide risk or who are likely to require psychiatric hospitalization during the course of the study.
13. Are unable to fully understand the potential risks and benefits of the study and give informed consent.

Planned Duration of the Study

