Natural Killer (NK) cell count*	NK count	Immunological function	5 minutes	X*		Outcome
Reactions to Research Participation Questionnaire	RRPQ	Experience of being participant	5-10 minutes		X	Process
Self-Expansiveness Level Form	SELF	Self-boundary	5 min.		X	Process
Spielberger State Trait Anxiety Inventory ^a	STAI	Anxiety	5-10 min.		X	Outcome
States of Consciousness Questionnaire	SCQ	Rating of altered states of consciousness	25 min		X	Process
Structured Clinical Interview for DSM-IV	SCID	Past and present psychiatric health	50-120 min.	X		Screening

#Primary outcome measure *Assessed via blood draw

Visit Descriptions: Psychotherapy and Assessment

Subject Numbering

Prior to enrollment, subjects will be tracked with their initials and a screening number assigned sequentially starting at “001”. Subjects who meet the study admission criteria will be enrolled into the study and will be assigned a 4-digit subject number. The first two digits identify the study site. The next two digits identify the subject within the site and will be assigned sequentially, with 01 corresponding to the first subject enrolled, e.g. the first enrolled subject will be 0101, second 0102, etc.

Screening and Baseline evaluation (Visits #1 to #3)

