After giving written consent, participants will be screened for presence of anxiety and for the presence of any psychiatric conditions that preclude study participation, such as psychosis. The principal investigator will conduct the screening evaluation in his office. The Structured Diagnostic Clinical Interview (SCID) will be used for diagnosing anxiety and detecting any conditions that preclude study participation, and the Mini Mental State Evaluation (MMSE) will be used to determine mental state and competency to take part in the study. Only participants with MMSE scores of 27 or higher will be eligible for study participation. The Hospital Anxiety and Depression Scale (HADS) will be used to quantify anxiety. Only people who are diagnosed with anxiety via SCID or who have a HADS Anxiety score of eight (8) or higher will be eligible for study participation. Once it is determined that participants meet study eligibility criteria, participants will complete or undergo additional assessments of anxiety and depression, quality of life and functional status, described above. The primary caregivers will complete the HADS. The investigators will also provide participants with daily pain and medication diaries and instructions on how to complete them. Participants will begin completing daily pain and medication diaries starting after baseline analysis.

Randomized blinded Study phase

Randomization

Upon enrollment into the study, participants will be assigned to one of two conditions, active placebo (4 mg psilocybin) or full experimental intervention (25 mg psilocybin). Active placebo in this study is a low dose of the investigational drug that will not produce the unique effects of psilocybin. Participants have a 66% chance of assignment to the full experimental intervention, with six of nine participants will be assigned to receive the full experimental intervention and three will be assigned to receive active placebo. The internal review committee coordinator at the study site will generate and maintain the randomization code and procedure. Condition assignment will be maintained from study enrollment up through the course of the study, as there is no crossover design. If there is an adverse event or other emergency requiring knowledge of participant's condition assignment, as when pharmacological intervention is necessary, the blind may be broken for an individual participant.

Introductory Psychotherapy Session (Visits #4 and #4.5)

Psychotherapy

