Rescue medication will only be used if an individual is endangering him or herself or others, or at the discretion of the investigator. The use of prescribed rescue medicines during an experimental session is contraindicated because it can interrupt the therapeutic process, although it would not be expected to cause any physical harm to the subject. The goal of the process is to confront fears and to experience them fully as a means of coping with them, and participants are likely to feel anxious during the course of the experimental session.

The investigators will query subjects about suicidal ideation or intent during screening, and prior to each psilocybin session. Participants who evidence suicidal ideation or intent will be withdrawn from the study and referred to appropriate psychiatric care.

If a psychiatric hospitalization is necessary, participants will be admitted to the study site, which is on the same campus as the clinic. The hospital will be informed in advance about the study.

Medical Emergencies

Basic emergency equipment is available in the cancer center. The principal investigator's office is located in the study site, on the same grounds as the clinic. The hospital will be informed in advance about the nature of this study.

The investigators will assess blood pressure at least five times during the experimental session; immediately prior to drug administration, and hourly for the next three hours. The investigators will make more frequent measures if in their judgment these are warranted. The clinic will have the appropriate medications and equipment to treat hypertension or cardiac problems if they should arise. The slight elevations in blood pressure or heart rate after psilocybin are not expected to cause any problems or cause any adverse events requiring medical intervention.

An adverse event (AE) is defined as any untoward medical occurrence in a patient or clinical investigation subject administered a pharmaceutical product at any dose that does not necessarily have to have a causal relationship with this treatment. An AE can, therefore, be any unfavorable and unintended sign (including an abnormal laboratory finding, for example), symptom, or disease temporally associated with the use of an investigational product, whether or not considered related to the investigational product. This definition includes concurrent illnesses or injuries and exacerbation of pre-existing conditions.

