As is true of the pharmacologically similar compound LSD, psilocybin use is associated with transient and sometimes prolonged psychotic states in users (Benjamin 1979; Halpern and Pope 1999). Researchers who reviewed case series and reports that associated LSD or serotonergic psychedelics more generally with subsequent occurrence of psychosis note that diagnosis of psychosis is made only after drug use, and not prior to it (Strassman 1984). After examining the literature, Strassman concluded that LSD might trigger psychotic episodes in people already vulnerable to psychosis but that it did not directly cause psychosis in people not susceptible to it. Two large studies surveyed clinicians or researchers who had conducted LSD research or LSD-assisted psychotherapy (Cohen 1960; Malleson 1971) and found the prevalence of psychiatric symptoms after participation to be very low. None of the participants in recent psilocybin studies experienced psychotic states, though some participants exhibited transient paranoia or some loss of insight into the situation during the course of psilocybin effects (Gouzoulis-Mayfrank et al. 1999b; Griffiths et al. 2006; Vollenweider et al. 1997). These findings suggest that while psilocybin can provoke psychosis or other psychiatric symptoms in a very small percentage of people, it does not do so often, and that receiving a psychedelic drug as part of a research study is extremely unlikely to trigger transient or persistent psychosis. The occurrence of transient or persistent psychosis can be prevented or further reduced by screening subjects on the basis of past and current mental health. Subjects with a personal or family history in first-degree relatives of psychosis (bipolar disorder or schizophrenia), or suicide attempts will be excluded from this study.

If a participant should become psychotic or suicidal for a time exceeding the duration of drug effects and the investigators are unable to ameliorate these symptoms, arrangements will be made for him or her to be admitted to the nearest inpatient psychiatric facility at the clinic.

Chronic neuropsychological effects

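### The risk section excludes people for suicide attempts, but no numbered eligibility criterion names an attempt and the stated suicidality questions do not ask about one

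*Protocol*

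**What the plan says.** **Risk section (Psychosis, suicidal thoughts or impulses).** The text explains that psychosis "can be prevented or further reduced by screening subjects on the basis of past and current mental health". The next sentence begins with a personal history and goes on: "family history in first-degree relatives of psychosis (bipolar disorder or schizophrenia), or suicide attempts will be excluded from this study". The wording is flat and leaves the investigator no discretion.

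**Exclusion Criteria.** There are 13 numbered items. Item 12 is the only one that mentions suicide: "Are reasonably judged to present a serious suicide or homicide risk or who are likely to require psychiatric hospitalization". Item 1 covers the candidate's own bipolar or psychotic disorder. Item 3 covers psychiatric disorders in first-degree relatives, with mood disorders exempted. Neither mentions attempts, and nor do the 10 inclusion criteria.

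**Acute Psychological Distress.** "The investigators will query subjects about suicidal ideation or intent during screening, and prior to each psilocybin session". The consequence follows: "Participants who evidence suicidal ideation or intent will be withdrawn from the study". Past attempts are not named.

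**How enrolment is decided.** Sample Population and Subjects opens with "The study will enroll nine (9) individuals with the following criteria listed below", and Subject Numbering says "Subjects who meet the study admission criteria will be enrolled into the study". The sample enrolment form in Appendix B has the principal investigator review the screening and baseline source data together with the inclusion and exclusion criteria.

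**The concern.** The protocol states an eligibility rule in its risk narrative and leaves it out of the list that investigators screen from. The rule concerns history. The nearest listed item concerns judged present or future risk. The two do not select the same people.

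At stake is whether a particular kind of candidate is enrolled and dosed with a drug that the protocol itself says can provoke psychiatric symptoms in a small percentage of people. The risk section offers the exclusion as part of its account of how that risk is contained. A reader weighing risk, such as an ethics board member, would take the safeguard to be in force. An investigator working down the numbered criteria would find no prompt to apply it.

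**Working it through.** No sample size, power or alpha figure is involved, so the check is a comparison of texts.

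**1. Count the listed items that name a suicide attempt.**

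| List | Items | Name an attempt | Mention suicide at all |
|---|---|---|---|
| Exclusion Criteria | 13 | 0 | 1 (item 12, as judged risk) |
| Inclusion Criteria | 10 | 0 | 0 |
| Total | 13 + 10 = 23 | 0 | 1 |

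**2. Compare the two tests on the same candidates.**

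| Candidate | Exclusion 12 | Risk section |
|---|---|---|
| Past attempt, judged a serious current risk | Excluded | Excluded |
| Past attempt, hospitalization judged likely | Excluded | Excluded |
| Remote attempt, no ideation, no judged serious risk, hospitalization not likely | Not excluded | Excluded |
| No attempt, judged a serious current risk | Excluded | Not addressed |

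The third row is the gap. It is confined to people for whom the exclusion 12 judgement comes out negative, but it is not empty.

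**3. See whether other text closes the third row.**

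- *Suicidality questions.* These ask about ideation or intent. A person with neither is not caught, whatever their history.
- *SCID.* Screening and Baseline evaluation says that it "will be used for diagnosing anxiety and detecting any conditions that preclude study participation". Appendix A describes it as an interview for diagnosing lifetime and current disorders. An attempt is not itself a diagnosis. If the interview brings one to light, the list gives it weight only through exclusion 12.
- *Exclusion 3.* This concerns relatives' disorders. A relative's attempt without a qualifying disorder is outside it.
- *Sample forms in Appendix B.* The baseline pages have no field for past attempts. A suicide-risk code appears for Visits 4 to 6, after enrolment, and records risk rather than history. These are labelled sample drafts, so this only supports the points above.

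**4. Establish which text the enrolment check uses.** The sample enrolment form refers to the inclusion and exclusion criteria, and the Visit 5 form asks again whether those criteria are still met. Both point to the numbered lists, where the rule is absent.

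**5. Read the scope of the risk-section sentence.** It starts with personal or first-degree family history and ends with suicide attempts. The closing words can attach to the candidate alone, or to the candidate and first-degree relatives. No period is given. Under either reading, the numbered list lacks the rule.

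**The case against.** The strongest reply is that nothing here is contradictory. The exclusion list says that people with the listed conditions are kept out. It does not say that only they are. The inclusion criteria are worded as necessary, not sufficient. Subject Numbering speaks of admission criteria without tying them to the numbered items. The risk section can then be read as adding a stricter rule, and it does so elsewhere: under Chronic neuropsychological effects it relies on excluding people who report HPPD after earlier hallucinogen use, which is not in the list either. An investigator who applies the whole protocol excludes the person with a past attempt.

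This stands as far as it goes. A reader might infer that the protocol gives opposite answers on the same person, or that the list permits enrolment after an attempt. The text supports neither, because both inferences need the list to be exhaustive and it does not claim to be. What remains is an omission: a mandatory rule sits outside the list that the enrolment form checks, and no stated question elicits the fact that it depends on.

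A second reply is that exclusion 12 already deals with the matter, since a careful psychiatrist would weigh a past attempt. It is right that an attempt can inform that judgement, so it would be wrong to say that the list gives it no role. But informing a judgement differs from a flat exclusion, and the risk section states the latter.

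A third reply is that other safeguards limit the consequences: a two-hour psychiatric evaluation at Visit 3, source-data review before enrolment, suicide-risk ratings at Visits 4 to 6, and overnight nursing with therapists on call. These bear on how serious the gap is. They do not supply the missing criterion.

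**Conclusion.** The point holds as an internal inconsistency in eligibility. The risk section excludes for suicide attempts, 0 of 23 numbered criteria name one, and the stated questioning covers ideation and intent only. The people affected are those with a past attempt who are not judged to be at serious risk or likely to need psychiatric hospitalization. They pass the numbered list, although the risk section keeps them out.

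This rests on two readings: that investigators screen mainly from the numbered list, as the sample forms suggest, and that the risk-section sentence is meant as a rule and not as loose description.

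Two further inferences are not supported. A reader might take the attempts to mean the candidate's own only, but the sentence can equally cover first-degree relatives, and that is for the sponsor to settle. A reader might also infer a measurable risk of harm. The protocol gives no rate of past attempts and no outcome data for such people, so no probability of enrolment or harm can be stated. No estimate, endpoint or analysis is touched. The correction is worth making because it concerns participant safety and costs very little.

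**What to change.** 1. Add a history of suicide attempt to the numbered exclusions, for example as a further clause in exclusion 12.
2. Ask about past attempts at the Visit 3 psychiatric evaluation, and record the answer before the enrolment decision.
3. Have the sponsor confirm whether attempts by first-degree relatives also exclude, and over what period an attempt counts. If relatives' attempts count, bring exclusion 3 into line. Word the risk section to match.

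The cost is one or two clauses, one clarification and one recorded question. Any candidate with a past attempt is lost, which the risk section already intends. Deleting the phrase from the risk section would also make the two places agree, but it would remove a stated safeguard and should be done only if the sponsor never meant the exclusion to apply.

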All outcome measures selected for this study were chosen because they are well-recognized in the literature and because they are or will be used in related pilot studies, allowing comparison across these investigations. The primary outcome measure for this study will be the HADS anxiety score. The investigators will also measure anxiety with the STAI and the HAM-A. The investigators will assess depression with HADS depression scores and with the HAM-D. Participant beliefs about life purpose and spirituality will be measured with the FACIT-Sp, spirituality in relation to self-concept by the SELF, and quality of life will be assessed with the EORTC-QLQ-C15. Daily pain levels will be assessed via participant response on a visual analog scale, and daily pain and anxiety medication use will serve as an indirect measure of anxiety and experienced pain. Natural killer cell counts will serve as a measure of innate immune system function.

All participants will be screened via SCID and HADS, as described above in “Screening”. The investigators will also use MMSE scores to assess study eligibility and mental competence throughout the course of the study.

The SCQ will serve as a process measure, assessing presence and degree of effects of psilocybin, and the SELF will serve as a process measure of self-boundary change. The KRPS, a measure frequently employed in studies of people with cancer, will serve as a means of rating performance status.

Table 1: List of assessments for use in this study. Time listed in minutes.

Assessment	Abbreviation	Measure of	Time needed	Clinician rated	Participant Self-rated	Purpose of Assessment/Measure
Daily Medication Diary	--	Anxiolytic & pain management meds	5 min		X	Outcome
Daily Pain Level Diary	--	Daily pain levels	5 min.		X	Outcome
Europ. Organiz. For Research and Treatment of Cancer; Quality of Life Questionnaire-C15	EORTC QLQ-C15	Global quality of life	5-10 minutes.		X	Outcome
Functional Assessment of Chronic Illness Therapy-spirituality	FACIT-Sp	Spiritual or life purpose beliefs	5 min.		X	Outcome
Hamilton Anxiety Rating Scale	HAM-A	Anxiety	5-10 min	X		Outcome
Hamilton Depression Rating Scale	HAM-D	Depression	5-10 min	X		Outcome
Hospital Anxiety and Depression Scale#	HADS	Anxiety + Depression	5-10 min.		X	Screening & Outcome
Karnofsky Performance R__ Scale	KPRS	Everyday life function	5 minutes	X		Supplemental
Mini Mental State Examination	MMSE	Mental status / competency	15 minutes	X		Screening, continued eligibility
Natural Killer (NK) cell count*	NK count	Immunological function	5 minutes	X*		Outcome
Reactions to Research Participation Questionnaire	RRPQ	Experience of being participant	5-10 minutes		X	Process
Self-Expansiveness Level Form	SELF	Self-boundary	5 min.		X	Process
Spielberger State Trait Anxiety Inventory ^a	STAI	Anxiety	5-10 min.		X	Outcome
States of Consciousness Questionnaire	SCQ	Rating of altered states of consciousness	25 min		X	Process
Structured Clinical Interview for DSM-IV	SCID	Past and present psychiatric health	50-120 min.	X		Screening

#Primary outcome measure *Assessed via blood draw

Visit Descriptions: Psychotherapy and Assessment

Subject Numbering

Prior to enrollment, subjects will be tracked with their initials and a screening number assigned sequentially starting at “001”. Subjects who meet the study admission criteria will be enrolled into the study and will be assigned a 4-digit subject number. The first two digits identify the study site. The next two digits identify the subject within the site and will be assigned sequentially, with 01 corresponding to the first subject enrolled, e.g. the first enrolled subject will be 0101, second 0102, etc.

Screening and Baseline evaluation (Visits #1 to #3)

After giving written consent, participants will be screened for presence of anxiety and for the presence of any psychiatric conditions that preclude study participation, such as psychosis. The principal investigator will conduct the screening evaluation in his office. The Structured Diagnostic Clinical Interview (SCID) will be used for diagnosing anxiety and detecting any conditions that preclude study participation, and the Mini Mental State Evaluation (MMSE) will be used to determine mental state and competency to take part in the study. Only participants with MMSE scores of 27 or higher will be eligible for study participation. The Hospital Anxiety and Depression Scale (HADS) will be used to quantify anxiety. Only people who are diagnosed with anxiety via SCID or who have a HADS Anxiety score of eight (8) or higher will be eligible for study participation. Once it is determined that participants meet study eligibility criteria, participants will complete or undergo additional assessments of anxiety and depression, quality of life and functional status, described above. The primary caregivers will complete the HADS. The investigators will also provide participants with daily pain and medication diaries and instructions on how to complete them. Participants will begin completing daily pain and medication diaries starting after baseline analysis.

Randomized blinded Study phase

Randomization

Upon enrollment into the study, participants will be assigned to one of two conditions, active placebo (4 mg psilocybin) or full experimental intervention (25 mg psilocybin). Active placebo in this study is a low dose of the investigational drug that will not produce the unique effects of psilocybin. Participants have a 66% chance of assignment to the full experimental intervention, with six of nine participants will be assigned to receive the full experimental intervention and three will be assigned to receive active placebo. The internal review committee coordinator at the study site will generate and maintain the randomization code and procedure. Condition assignment will be maintained from study enrollment up through the course of the study, as there is no crossover design. If there is an adverse event or other emergency requiring knowledge of participant's condition assignment, as when pharmacological intervention is necessary, the blind may be broken for an individual participant.

Introductory Psychotherapy Session (Visits #4 and #4.5)

Psychotherapy

The therapist-investigators will conduct at least one introductory psychotherapy session no later than seven days after the baseline evaluation. Introductory sessions will provide up to six hours of preparation, including one to two sessions of psychotherapy that will last from 90 to 120 minutes, and working with a hypnotic induction CD. Introductory sessions may be presented by one or both of the investigator-therapists. Introductory psychotherapy will occur after participants are assessed for continued study eligibility and complete measures of anxiety and depression.

After introductions are shared between the participant and the therapist-investigators, at least one and possibly both of the investigators will discuss the participant's lifespan and psychological development, any goals or desires they have, their spiritual beliefs or world-view and any beliefs about death or the afterlife, and any past experiences that share some similarities with psilocybin-assisted psychotherapy, such as any past use of classical hallucinogens/psychedelics and any past mystical or transformative experiences. The therapist-investigators will teach mindfulness techniques, such as diaphragmatic breathing with cognitive-behavioral stress management in a spiritual context. The therapist-investigators will inform participants of what to expect during a psilocybin-assisted psychotherapy session and they will address any specific hopes, fears or specific goals the participant has in respect to the upcoming psilocybin-assisted psychotherapy sessions. The investigators will also provide participants with a CD containing procedures for hypnotic induction, and if there is time available, one or both therapist-investigators will review and discuss the content of the hypnotic induction CD. The investigators will present participants with instructions and food, alcohol or medication restrictions for the time starting 24 hours prior to a psilocybin-assisted psychotherapy session, and the participant will be encouraged to ask questions about these instructions. A second introductory session will occur if the investigators deem it necessary. The investigators will meet with any significant other who plans to accompany the participant for part of a psilocybin-assisted session and the overnight stay, if applicable.

Introductory psychotherapy sessions will be recorded to audio and video. No identifying information save assigned participant subject number will be written on any session recordings. Participants will have an opportunity to review session recordings.

Assessment

Participants will undergo assessment with MMSE to ensure their continued eligibility prior to each introductory psychotherapy session. They will complete the HADS and STAI prior to the first introductory session, and the FACIT-SP and EORTC-QLQ-C15 prior to the second introductory session. They will complete daily pain and medication diaries during this time period.

Psilocybin-Assisted Psychotherapy (Visit #5, Visit #8)

Psychotherapy

There will be two psilocybin-assisted psychotherapy sessions scheduled to occur seven to fourteen (14) days apart, on study visits #5 and #8. Both psilocybin-assisted psychotherapy sessions will take place at the study site and will be staffed by the two investigator-therapists, one male and one female. Procedures for the two drug-assisted sessions will be identical. During the second experimental session, the participant and therapist-investigators may discuss material or experiences from the first psilocybin-assisted session.

Participants will arrive at the Cancer Center at approximately 9:00 AM. Participants will be instructed to refrain from alcoholic beverages starting 12:00 on the night prior to each psilocybin-assisted session, and to eat only a light breakfast on the morning of the

session. On arrival, they will have a blood draw for the assessment of liver function and metabolism, and they will have urinary drug and pregnancy screens. After undergoing these screens, one of the investigators will conduct the MMSE, and the participant will complete outcome measures. He or she may return completed daily pain and medication diaries at this point. Results from laboratory tests will be available approximately 45 minutes after the blood draw, and significantly abnormal results will result in rescheduling of psilocybin session or withdrawing the subject from the study. Positive pregnancy screen will result in withdrawal from the study.

